Families who qualify and are interested in participation will be scheduled for their laboratory visit. Parents will be given as much time as they would like to decide whether to make an appointment for the laboratory visit, however, it will be noted that this visit must occur while their children remain within the age range or no longer than 6 months after their CARE V2 visit. At the start of the laboratory visit, participants will be guided through the consent form by the staff member administering consent procedures. Note that the family will already have had access to the consent form as our consent form will be emailed ahead of potential participation. After discussing informed consent, the staff member will note that they can decide to participate today or consider participation at a later date. The staff member will remind the family that their decision to participate (or not participate) will have no effect on the care they may be receiving through Washington University Medical Center. The staff member will ask the family if they would like to be left alone in the room to discuss participation.

In the unlikely event that a parent completes all or part of questionnaires but does not show up for their laboratory visit, the family will be contacted twice. If the family does not respond to contact or says that they are no longer interested in participation, their questionnaire responses will be destroyed. No data from any family will be exported from RedCap to laboratory databases until informed consent is signed in the laboratory. If a family chooses not to sign consent, all questionnaire data will be destroyed as described previously.

Participants are able to stop participating at any time. In the event that a participant declines to continue participating, the session will be stopped and the participant will be compensated for their time in proportion to how much of the session was completed (e.g., if 1 hour of a 3 hour session was completed, the participant would be compensated \$25). There are no potential adverse consequences to ending participation before the end of the study, thus no further follow up or care is needed should the participant opt out of further research activity with the lab.

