4.3 Will any participants receive a placebo in place of standard therapy?
 No

5. Privacy & Confidentiality

5.1 Indicate your plans to protect the privacy interests of the participants during the conduct of the study (check all that apply):

- Only the minimum necessary private information is collected for the purposes of the study
- Any procedures or interventions conducted as part of the study will be conducted in private setting to the extent possible
- Recruitment/consent will occur in a private setting
- Participants will be able to ask questions in a private setting

5.2 Are you collecting or using the Social Security Number of any participants for any purpose?
Yes

5.2.a Provide the intended usage of SSN:
• **To provide compensation to participants**

5.3 Project uses paper or hard copy consents, surveys, data collection forms, research subject binders, or other hard copy materials (check all that apply):
Yes

- All materials are stored in secured environment
- Access is limited to research team members only

5.4 Project collects, stores and/or transmits electronic data on mobile devices, desktop computers, servers including cloud servers, email, or any other information in electronic form (check all that apply):
Yes

- Data in Redcap
- Password protected
- Access is limited to research team only

5.5 Project collects or uses biologic specimens (check all that apply):
Yes

- Stored in secured environment
- Access is limited to research team only
- Coded and the identifiers or key is stored separately from the data
- Transported securely/shipped with tracking mechanism

5.6 Identify any additional protections in place for data and or samples (check all that apply):

- Formal research staff training process

Statistical Analyses: All analyses will be conducted with data collected from the timepoint of our assessment of pain sensitivity. However, we will also leverage our longitudinal data of early-life adversity, psychopathology, and biological measures aggregating the data using the worse or maximum, the timepoint prior to our measurement of pain sensitivity, and the slope up to the timepoint of assessment of pain sensitivity. The relatively small sample size of this project (n=40) is expected to produce preliminary effect sizes to guide hypotheses for future NIH applications.

Aim 1: To test the relationships between pain and both early-life adversity and psychopathology symptoms.

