Hypothesis 1: Early-life adversity will predict both higher pain sensitivity and psychopathology symptoms. Hypothesis 2: Pain and psychopathology symptoms will be positively associated.

Analysis: We will examine early-life adversity, based primarily on the ACES and RDAS, with both pain sensitivity and psychopathology symptoms individually. We will use Pearson's correlations between each of our measures of pain (temperament, self and parent-reported pain impairment, and experimental pain sensitivity).

Aim 2: To examine the relationship between emotion dysregulation and pain.

Hypothesis 1: Biological and parent-reported emotion dysregulation will be positively associated with pain sensitivity. Analysis: We will examine the relationship of salivary cortisol and parent-reported emotion dysregulation with multi-modal assessments of pain using Pearson's correlations. We will use also use regression analyses with leading factors of pain identified from variable reduction methods as dependent variables, and each of the emotion regulation measures as independent variables and control for covariates.

Aim 3: To experimentally test the role of parental support in the relationships between early-life adversity, biological and parent-reported emotion dysregulation, pain, and psychopathology.

Hypothesis 1: Parental support, assessed through parent-report of attachment and parent-child neural and behavioral synchrony measured through fNIRS and video coding, will buffer the effects of early-life adversity on pain sensitivity and psychopathology symptoms. Analysis: We will examine three measures of parent-support 1) the difference in child report of experimental pain sensitivity (pain intensity ratings and cold pain tolerance) and cortisol from the parent handholding vs. alone conditions in the parent-report cold pressor task from the current project; 2) parent report of parental support primarily using the CCNES and PRQ; and 3) dyadic behavioral and brain synchrony from the CARE R01. We will employ multivariate regression models to test the effects of early-life stress and emotion dysregulation, individually, as an independent variable on both pain sensitivity and psychopathology as the dependent variables with parent-support variables as a moderator.

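### Aim 2 correlates salivary cortisol with pain across children without adjusting for the clock time of sampling, and no covariate named in the supplied documents covers it.

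*Combined protocol and SAP*

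**What the plan says.** The Aim 2 hypothesis is that "Biological and parent-reported emotion dysregulation will be positively associated with pain sensitivity". Its analysis starts with: "We will examine the relationship of salivary cortisol and parent-reported emotion dysregulation with multi-modal assessments of pain using Pearson's correlations". The next sentence adds regressions on leading pain factors, with "each of the emotion regulation measures as independent variables and control for covariates". No covariate is listed.

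The opening paragraph of Statistical Analyses adds longitudinal summaries of earlier data, among them "biological measures aggregating the data using the worse or maximum, the timepoint prior to our measurement of pain sensitivity, and the slope" up to the pain assessment. Cortisol is not named there.

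Aim 3 uses cortisol differently, as a within-child difference: "cortisol from the parent handholding vs. alone conditions".

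On scheduling, item 1.12 says: "Families who qualify and are interested in participation will be scheduled for their laboratory visit". The limits it sets concern the child's age and the months since the second CARE visit, not the hour of day. The supplied text gives no number of saliva samples, no collection time and no sampling window. Item 1.1 lists a separate written protocol as an attachment, which is not among the supplied documents.

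On purpose, the plan says: "The relatively small sample size of this project (n=40) is expected to produce preliminary effect sizes to guide hypotheses for future NIH applications".

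**The concern.** Cortisol falls over the day. That is general physiology; the documents give no figure for it. A cortisol level taken in the morning from one child and in the afternoon from another differs partly because of the clock. A Pearson correlation across children cannot separate that part from the differences of interest.

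Two consequences follow if visit hours vary. The correlation is diluted. And if visit hour is itself related to pain or adversity, for instance through age or school attendance, a correlation can appear where there is none, or a real one can be hidden. Since the stated product of this study is preliminary effect sizes, a diluted or shifted correlation goes straight into the planning of later work. A shift of this kind does not average out as the sample grows.

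**Working it through.** **Figure in the plan.** The only relevant figure is n=40. It comes without alpha, power or effect size, so there is nothing to reproduce. Item 2.2.a expects 80 minors. I use 40, the figure in the analysis section; the shares, shrinkage and spurious correlations below do not depend on n.

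**Assumed inputs (none is in the documents).**
- Fall in log-cortisol per hour, b: 0.10, range 0.05 to 0.15.
- Visit times spread evenly over W hours: 8, with 5 and 4 as narrower cases. Item 1.12 mentions a 3-hour session as an example. In an 8-hour laboratory day (also assumed), start times could then span about 8 − 3 = 5 hours.
- Between-child SD of log-cortisol apart from clock time, s: 0.5, so s² = 0.25.

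**Formulas.**
- Variance from clock time: b²W²/12.
- Share of cortisol variance: v = (b²W²/12) / (b²W²/12 + s²).
- Observed correlation = true correlation × √(1 − v).
- With no true association, spurious r = −√v × correlation of visit hour with pain. I assume 0.3 for the latter.

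**Results.**

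| W (h) | b | Clock variance | v | Shrinkage factor | Spurious r |
|---|---|---|---|---|---|
| 8 | 0.05 | 0.0133 | 0.0133/0.2633 = 0.051 | 0.97 | −0.07 |
| 8 | 0.10 | 0.0533 | 0.0533/0.3033 = 0.176 | 0.91 | −0.13 |
| 8 | 0.15 | 0.1200 | 0.1200/0.3700 = 0.324 | 0.82 | −0.17 |
| 5 | 0.10 | 0.0208 | 0.0208/0.2708 = 0.077 | 0.96 | −0.08 |
| 4 | 0.10 | 0.0133 | 0.0133/0.2633 = 0.051 | 0.97 | −0.07 |

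The spurious r is negative if later visits go with more pain. If they go with less pain the sign reverses, which is the direction that Aim 2 hypothesises.

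**Effect at n=40** (Fisher z, two-sided alpha 0.05 assumed). A true r of 0.43 has power 0.80 when v = 0, 0.75 at v = 0.1, 0.69 at v = 0.2 and 0.63 at v = 0.3. With no true association, v = 0.2 and a 0.3 correlation of hour with pain, the test rejects about 13% of the time instead of 5%.

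**Maximum and slope, if applied to cortisol.** I assume three visits, independent visit hours, and half of the remaining variance stable within child. The correlation of the observed slope with the slope free of clock time is then √((1 − v)/(1 + v)). Simulation gives the maximum.

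| v | Single visit | Maximum | Slope |
|---|---|---|---|
| 0.1 | 0.95 | 0.94 | 0.90 |
| 0.2 | 0.89 | 0.89 | 0.82 |
| 0.3 | 0.84 | 0.83 | 0.74 |

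The slope suffers most, because it carries the clock-time error of more than one visit while differencing removes the stable part of the child's level.

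**The case against.** The strongest reply is that the supplied form describes no saliva procedure at all, so silence on clock time proves little; the separate protocol may fix the hour or record it. This stands. A reader might infer that samples are taken without a recorded time, or that families choose the hour. The documents support neither: item 1.12 says only that a visit will be scheduled.

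A second reply is that covariate adjustment is already planned. That is true of the regressions, and the plan does not rank them below the correlations. But the covariates are unnamed, and the Pearson estimates would be reported unadjusted whatever the regressions contain.

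Third, the plan does not say whether Aim 2 uses a cortisol level or a reactivity score. The figures above are for a level. The one cortisol contrast that the plan defines, in Aim 3, is largely protected from between-child differences in visit hour.

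Fourth, the dilution is small beside sampling error. At n=40 an observed r of 0.30 has a 95% interval of about −0.01 to 0.56, and over 4 to 5 hours at 0.10 per hour the dilution is only 3 to 4%. This is fair on size. It does not argue against an adjustment that costs almost nothing, and a wider interval is no answer to a shifted estimate.

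**Conclusion.** The concern holds in a limited form. Aim 2 specifies unadjusted correlations for a measure that varies with the hour, and nothing in the supplied text fixes that hour or names it as a covariate. If hours differ, an 8-hour spread costs 3 to 18% of the size of a correlation (9% at 0.10 per hour). The cost is about 4% over 5 hours and 3% over 4 hours, both at 0.10 per hour. These figures rest on the assumed hourly fall and SD.

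A reader might go further and conclude that the cortisol results are confounded. The documents do not support that. Confounding needs visit hour to be related to pain or adversity, and no such relation is shown. The spurious r of about −0.07 to −0.17 (8-hour spread) is what would follow from an assumed correlation of 0.3. Nor do the documents say that the maximum or slope will be taken of cortisol. That is a fair inference, since cortisol is the biological measure named in Aim 2, but it remains an inference.

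**What to change.** - Record the clock time of every saliva sample, if the separate protocol does not already require it.
- In Aim 2, report partial correlations of cortisol with pain adjusted for sampling time, in place of the unadjusted ones.
- Name sampling time as a covariate in the cortisol regressions.
- If the maximum or slope is applied to cortisol, first adjust each visit's value for its sampling time. This works only where the earlier CARE visits logged the time; where they did not, state the limitation.
- Optionally, hold the pain visits in one part of the day. This can be dropped if it slows recruitment.

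The cost is one time field per sample, a few lines of analysis text and one degree of freedom. At n=40 the standard error on the Fisher z scale goes from 1/√37 = 0.164 to 1/√36 = 0.167. The time field should be in place before further samples are taken, because a time that was never recorded may not be recoverable.

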4.19 Will any external monitors require access to this study in Epic?
No

4.21 Mark all that apply to your study:

1. Protocol

1.1 Is there a separate, written protocol that will be submitted in addition to this form? (Note: a grant application is not considered to be a protocol)
Yes

Attachment Name	Category	Version	Date Attached
CARE Extension Project IRB Protocol_updated 1.23.2025.rtf	Intervention: Separate Written Protocol	9	02/03/25

1.1.a Who initiated/provided the protocol?
WashU Investigator

1.1.b Protocol#:

1.1.c Protocol Version#:

1.1.d Protocol Date
12/13/2023

1.1.e Provide a list of the amendments for this study (this may be left blank if none). Any amendments previously listed should not be removed.

1.2 Select up to three key words below that best describe this research study:

- Psychiatry
- Psychology

1.3 Provide a short summary/abstract of the purpose and procedures of the study proposed in this IRB application.

- DO NOT include information on studies not proposed in this application.
- Use LAY terminology only. This must be easily understandable by IRB community members and nonscientists.
- DO NOT cut and paste technical abstracts from source of support applications that may not be understood by a general audience.

This study seeks to investigate the impacts of adversity in early life pain and psychopathology symptoms in middle childhood. Specifically, we will investigate children aged 5 – 9.5 years old who have experienced a parental separation, divorce, or breakup, and a matched control group. We will use a Cold Pressor Test to assess experimental pain sensitivity with and without parental support. Additionally, we will use neuroimaging methods including, an optional fNIRS protocol to characterize changes in patterns of brain activities. We will also employ the use of surveys and questionnaires, to investigate pain and psychopathology symptoms, as well as parental support. By imaging the neural circuitry supporting these different aspects in children and their caregivers, the proposed research will explore the impacts of family related stress on the developing brain.

1.8 Check all materials/methods that will be used in recruiting participants:

- Ads/Brochures/Posters/News Release/Fliers
- Email or letters

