1.14 Will participants be randomized?

Yes

1.15 Will any of the following be used to collect information from the participant or others?

- Screening questions or screening/eligibility questionnaires
- Surveys
- Questionnaires
- Stimuli
- Any other written assessments

Yes

Attachment Name	Category	Version	Date Attached
PHQ-9_PatientHealthQuestionnaire.pdf	Subject Data Collection Instruments	1	05/31/24
ASRI 4R.pdf	Subject Data Collection Instruments	1	05/31/24
PRQ.docx	Subject Data Collection Instruments	1	05/31/24
AssessmentOfParentAndChildAdversity_(APCA).pdf	Subject Data Collection Instruments	1	02/26/24
Difficulties in Emotion Regulation Scale.pdf	Subject Data Collection Instruments	1	02/26/24
Drug Use Screening Inventory (DUSI-R).pdf	Subject Data Collection Instruments	1	02/26/24
GAD-7_GeneralizedAnxietyDisorders.pdf	Subject Data Collection Instruments	1	02/26/24
ACES_PEARLS.pdf	Subject Data Collection Instruments	1	02/26/24
Pain Sensitivity Questionnaire.pdf	Subject Data Collection Instruments	1	02/26/24
Macarthur SES Demographics.pdf	Subject Data Collection Instruments	1	02/26/24
Temperament in Middle Childhood (TMQ).pdf	Subject Data Collection Instruments	1	02/26/24
PROMIS Parent Proxy Numeric Rating Scale v1.0 - Pain Intensity 1a 1-8-2021.pdf	Subject Data Collection Instruments	1	02/26/24
Questionnaire of Unpredictability in Childhood (QUIC-parent).pdf	Subject Data Collection Instruments	1	02/26/24
Coping with Children's Negative Emotions (CCNES).pdf	Subject Data Collection Instruments	1	02/26/24
PROMIS Parent Proxy Bank v2.0 - Pain Interference 7-29-2016.pdf	Subject Data Collection Instruments	1	02/26/24
CONFLICT TACTICS SCALE.docx	Subject Data Collection Instruments	2	04/24/24

MacArthur Health and Behavior Questionnaire (HBQ).pdf	Subject Data Collection Instruments	1	02/26/24
Perceived Stress Scale (PSS).pdf	Subject Data Collection Instruments	1	02/26/24
PROMIS Parent Proxy SF v1.0 - Pain Behavior 8a 10-25-2019.pdf	Subject Data Collection Instruments	1	02/26/24

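### Aim 3 promises an experimental test of parental support, but the handholding-versus-alone contrast enters only as a moderator, so the supplied plan has no test of whether handholding weakens the adversity–pain association

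*Combined protocol and SAP*

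**What the plan says.** The Aim 3 heading in Statistical Analyses reads "To experimentally test the role of parental support in the relationships between early-life adversity" and the other constructs. Item 1.3 describes the manipulation: "We will use a Cold Pressor Test to assess experimental pain sensitivity with and without parental support".

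The Aim 3 Analysis lists three parent-support measures. The first is "the difference in child report of experimental pain sensitivity (pain intensity ratings and cold pain tolerance) and cortisol from the parent handholding vs. alone" conditions. The others are parent report (mainly CCNES and PRQ) and dyadic synchrony from the parent CARE study. One model family follows: early-life stress or emotion dysregulation, one at a time, as independent variable, "on both pain sensitivity and psychopathology as the dependent variables with parent-support variables as a moderator". No sentence makes condition a factor or D an outcome, and Aims 1 and 2 do not use condition.

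Three further passages limit the point:

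- Hypothesis 1 defines support differently: "Parental support, assessed through parent-report of attachment and parent-child neural and behavioral synchrony measured through fNIRS and video coding".
- Aim 3 does not say which score is pain sensitivity. Aim 1 refers to "each of our measures of pain (temperament, self and parent-reported pain impairment, and experimental pain sensitivity"), Aim 2 uses "leading factors of pain identified from variable reduction methods as dependent variables", and item 1.15 lists "Pain Sensitivity Questionnaire.pdf".
- Item 1.14 answers 'Yes' to randomization without saying what is randomized. Item 1.1 lists a separate written protocol that is not among the supplied documents.

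**The concern.** If handholding buffers adversity, children with more adversity gain more from it: the adversity slope is smaller with handholding than alone. That difference between slopes is what the experiment can estimate. The plan instead places the experimental contrast on the right-hand side of a model whose outcome may be one of the two scores from which the contrast was computed.

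The study's stated product is early effect sizes for later grant applications. For cold pressor pain, the only planned term that uses the handholding contrast would not report how far handholding reduces the adversity effect. A value near zero could be read as no buffering when buffering is complete. A non-zero value could be read as buffering when there is none on average.

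**Working it through.** **Inputs.** From the documents: n=40 (Statistical Analyses, introduction), two conditions per child, and the model form in Aim 3. The plan gives no effect size, SD, correlation or power, so it has no figure to reproduce. Everything else is assumed: adversity A with SD 1, residual SD 1 per condition, residual correlation ρ between conditions of 0.3, 0.6 or 0.8, two-sided 5% tests.

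**Step 1: the estimand.** For a score where higher means more pain, write alone = b·A + e1 and handholding = b(1−k)·A + e2, where k is the fraction of the adversity slope removed. Then D = alone − handholding = k·b·A + (e1 − e2). The slope of D on A is k·b, the reduction in slope. With both conditions observed, it equals the adversity × condition coefficient in a random-intercept model.

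**Step 2: the planned term.** Let M be mean pain. Then alone = M + D/2 and handholding = M − D/2. The planned model already contains D, so replacing M by M ± D/2 changes only the coefficient of D, by ±1/2. The A × D coefficient, its SE and its p-value stay the same. If the expectation of M given A and D is linear, as under joint normality, the A × D coefficient has expectation zero for every k.

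**Step 3: simulation with normal errors, b = 0.5, n=40.** Rejection rates for D on A are at ρ = 0.3 / 0.6 / 0.8.

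| True state | A × D mean; rejects | D on A mean | D on A rejects, OLS | D on A rejects, HC3 |
|---|---|---|---|---|
| Complete buffering (k=1) | 0.00; about 5% | 0.50 | 72 / 91 / 99% | 68 / 88 / 99% |
| Half buffering (k=0.5) | 0.00; about 5% | 0.25 | 25 / 39 / 66% | 24 / 37 / 63% |
| None (k=0) | 0.00; about 5% | 0.00 | about 5% | about 5% |

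The 95% CI half-width for D on A is roughly 2.02 × √(2(1−ρ)/39), or 0.38 / 0.29 / 0.20. The simulated averages are 0.39 / 0.29 / 0.21. With a weaker slope of 0.314, complete buffering is detected in 36 / 56 / 84% (OLS). Separate runs with other assumed inputs also left the A × D term between −0.01 and 0.01 for slope reductions from 0 to 0.8, at n=40 and n=80.

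**Step 4: departures from linearity.**

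- Exponential errors, complete buffering: A × D averages about −0.01 and rejects in 6 to 13%.
- Ceiling at +0.5 SD, complete buffering: A × D averages −0.11 / −0.16 / −0.23 and rejects in 20 to 25%. D on A averages 0.34 against a true 0.50.
- Same ceiling, no buffering, mean handholding benefit of 0.5 or 1 SD: D on A averages −0.07 or −0.12, so it is biased too.
- A between-dyad support trait that weakens the adversity slope equally in both conditions: A × D averages −0.08 to −0.38 and rejects in 11 to 39%. D on A averages about 0 and rejects in about 5%.
- Skewed (exponential) adversity with child-level buffering SD 0.5, ρ = 0.6: uncentred A × D averages −0.12 with no average buffering and −0.10 with complete buffering. Centring adversity brings it to about −0.05. D on A averages 0.00 and 0.50. Across the three correlations its type I error is 17 to 26% with OLS standard errors and 8 to 9% with HC3.

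**Step 5: condition order.** With balanced order, a 1 SD period effect and ρ = 0.6 (200 data sets), the SE of adversity × condition is 0.221 whether order is omitted or added as a main effect. It is 0.146 with order × condition, the same as when order is a covariate in the D regression.

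**The case against.** The strongest reply is that Hypothesis 1 is largely a between-dyad moderation hypothesis: it names attachment and synchrony, and the planned moderator model matches it. In the support-trait setting of Step 4, the planned term picks up that kind of moderation and D on adversity does not. This stands. A reader might infer that the moderator model is wrong and that D should be dropped from it. The documents do not support that: the two terms answer different questions, and what is missing is the second one, implied by the word *experimentally* in the aim.

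A reader might also infer that the planned coefficient is always zero. It is zero in expectation only when expected pain is linear in adversity and D. Additive errors of constant variance are not enough, as the exponential-error run shows. The departure there is small, and in none of the settings does the term measure average buffering.

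Nor can one conclude that the study has no such test anywhere. The separate protocol may specify one, and *multivariate* could mean both condition scores as joint outcomes, although the text does not say so. Pain sensitivity in Aim 3 may also mean a questionnaire score or a reduced factor. The point applies only when cold pressor pain is the outcome.

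Finally, the study is preliminary and both scores are collected, so the analysis could be run later. That lowers the consequence. It does not justify leaving the aim's own contrast without a stated analysis.

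**Conclusion.** The point holds as a gap in the supplied analysis text and is worth fixing. Aim 3's experimental contrast has no test of its own. For cold pressor outcomes, the one term that uses it does not estimate how much handholding reduces the adversity slope. That mismatch, and the identity of the coefficient across alone, handholding and mean pain, follow from algebra and need no assumed values. The zero expectation needs linearity. Every power figure, CI width and bias figure rests on assumed inputs.

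The CCNES/PRQ and synchrony moderators, the psychopathology models and the Aim 1 correlations are not affected. D remains a legitimate individual-difference moderator for psychopathology.

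**What to change.** Add the following as the experimental test for support measure 1, beside the moderator model:

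- Regress D on adversity, or equivalently fit adversity × condition with a random intercept per child. Do this separately for pain intensity and tolerance, signing D so that positive means less pain with handholding (for tolerance, handholding minus alone). Report the slope with a 95% CI from heteroscedasticity-robust standard errors such as HC3.
- If condition order varies, include order as a covariate in the D regression, or order × condition in the mixed model. If it is fixed, state that adversity × condition is confounded with adversity × period.
- Check ratings and tolerance for ceiling or censoring. If present, report the slope as possibly biased or use a censored model.
- Repeat with parent-reported emotion dysregulation in place of adversity. Do not regress the cortisol difference on cortisol-based dysregulation.
- Keep D as moderator for psychopathology. If it is kept for cold pressor outcomes, label that analysis exploratory and not the test of experimental buffering.
- State which score is pain sensitivity in Aim 3 and what the 'Yes' in item 1.14 refers to.

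Cost: wording only. Both condition scores are already needed to compute D, and sample and design do not change. The downside is one more analysis per outcome, with a wide CI at n=40.

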2.2 Will there be any minor participants?
Yes

2.2.a How many minor participants do you expect to consent or enroll under a waiver for this project?
80

2.2.b What is the age of the youngest minor participant?
5.0

2.2.c What is the age of the oldest minor participant?
9.5

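### The Aim 3 handholding-minus-alone moderator takes no account of which condition came first; if order varies between children, this dilutes the interaction

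*Combined protocol and SAP*

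**What the plan says.** - **Conditions.** The short summary (item 1.3) says: "We will use a Cold Pressor Test to assess experimental pain sensitivity with and without parental support".
- **The measure.** Under Statistical Analyses, Aim 3, the first of three parental-support measures is the difference in pain intensity ratings, cold pain tolerance "and cortisol from the parent handholding vs. alone conditions in the parent-report cold pressor task from the current project". The other two are parent questionnaires and dyadic synchrony.
- **The model.** Multivariate regressions relate early-life stress and emotion dysregulation to pain sensitivity and psychopathology, "with parent-support variables as a moderator". No order, period or sequence term is named. The phrase "and control for covariates" belongs to the Aim 2 regressions, and nothing equivalent is written for Aim 3.
- **Randomization.** The item "1.14 Will participants be randomized" is answered yes. The text does not say what is randomized. The two groups are children "who have experienced a parental separation, divorce, or breakup, and a matched control group", so group membership is observed, not assigned.
- **Sample size.** The statistical section says: "The relatively small sample size of this project (n=40) is expected to produce preliminary effect sizes". Item 2.2.a gives 80 expected minors. The two figures are not reconciled.

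**The concern.** A moderator needs one value per child, so each child must complete both conditions, one before the other. A second cold immersion may differ from the first through habituation, sensitisation or anticipation, whether or not the parent is present. The raw difference adds that effect to the support score of children who had handholding second and subtracts it from the score of those who had it first. Balancing the order protects the group average but not the individual scores, and Aim 3 uses the individual scores.

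The stated product of the study is preliminary effect sizes for later grant applications. A slope that is too small for an avoidable reason damages that product even if no significance test is emphasised.

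**Working it through.** The plan gives no alpha, power, effect size or SD for Aim 3, so there is no figure of its own to reproduce. The size below rests on assumptions.

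**Set-up.** Let S be a child's order-free support difference, scaled to SD 1. Let p be the second-minus-first immersion effect in those SD units. Let Z = +1 if handholding came second and −1 if it came first. The recorded difference is

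D = S + pZ.

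With balanced order, Var(D) = 1 + p², so the share of the variance of D that reflects S is 1/(1 + p²). With adversity or dysregulation as predictor X, the interaction slope should shrink by about that factor.

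**Assumed values.** True interaction 0.45, main effect of X 0.3, residual SD 1, two-sided 0.05, n = 40, balanced random order.

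| p | 1/(1+p²) | 0.45 × factor | Simulated raw slope | Raw power | Slope, D centred within order |
|---|---|---|---|---|---|
| 0 | 1.00 | 0.45 | 0.45 | about 66% | 0.45 |
| 0.25 | 0.94 | 0.42 | 0.42 | 63% | 0.45 |
| 0.5 | 0.80 | 0.36 | 0.36 | 57% | 0.45 |
| 1.0 | 0.50 | 0.225 | 0.22 | 39% | 0.45 |

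Repeat simulations agree to about 0.01 in the slope and 2 points in power. With D centred within order, power is about 65–66% at every p.

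**Why an order main effect is not enough.** The product term is XD = XS + pXZ. A main effect of Z leaves pXZ inside the interaction. In simulation, adding order alone gives 0.35 at p = 0.5 and 0.21 at p = 1.0, no better than the raw difference. Adding both Z and XZ restores 0.45.

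**If 80 children are enrolled.** Raw power is 93%, 88% and 68% at p = 0.25, 0.5 and 1.0, against about 94% with adjustment. The slope shrinks by the same factors, because a larger sample does not remove attenuation.

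**If order is the same for every child.** Then D = S + p for all children. The constant shifts the mean of D by p and leaves the interaction slope at 0.45 and power at about 67% for n = 40.

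**The case against.** **Order may not be what is randomized.** This stands as a limit. The form says only that there is randomization, and a separate written protocol is listed in item 1.1 whose procedures are not in the text reviewed. It may describe order assignment and the spacing of immersions and saliva samples. Counterbalancing described there would still not correct individual difference scores. A reader might infer that the analysis omits a factor known to be randomized; the documents do not go that far.

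**The order effect may be negligible.** No passage gives its size, and at 0.25 SD the loss is about 3 points of power. The claim is therefore a range, not a demonstrated loss. Since the section promises only preliminary effect sizes, the shrinkage of the estimate matters more than power.

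**The average support effect.** A reader might infer that a chance imbalance in order biases the estimated mean benefit of handholding. The plan lists no test or estimate of that mean; the difference appears only as a moderator. Chance imbalance under randomization would also be random error, not systematic bias.

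**Cortisol.** It is tempting to say that the second cortisol value must carry over from the first immersion. The text reviewed gives no sampling times, so this can be neither asserted nor excluded.

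**Scope.** Only one of three support measures is involved. The Aim 3 hypothesis itself defines support by parent-reported attachment and synchrony, so the aim as a whole does not fall with this measure.

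**Conclusion.** The concern holds conditionally. The Aim 3 text uses a raw condition difference as a moderator and names no term for order. If order varies between children, which is the most plausible reading of the randomization answer but is not stated, a common order effect shrinks the interaction by about 6%, 20% or 50% at order effects of 0.25, 0.5 or 1.0 SD (one minus 0.94, 0.80 and 0.50). These figures assume balanced order and an order effect common to all children; the slopes and power quoted also rest on the assumed true interaction of 0.45.

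If order is fixed, the moderator slope is not diluted. The average handholding effect is then inseparable from the order effect and should not be interpreted as parental support.

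A cheap correction exists and the plan should adopt it. The point does not show that Aim 3 is invalid.

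**What to change.** 1. State what the randomization in item 1.14 refers to. If it is the order of handholding and alone, say so, say how order is assigned, and record it for each child.
2. Before using any of the three differences (intensity, tolerance, cortisol) as a moderator, residualise it on order, that is, centre it within order. Alternatively, include both order and order-by-predictor terms in every Aim 3 model that uses the difference. Do not rely on an order main effect alone. A mixed model with condition, period and a random child intercept is also no substitute, because it estimates an average condition effect and supplies no child-level moderator.
3. If order is fixed, say so, and do not interpret the average difference as parental support.

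**Cost.** A sentence or two in the analysis section and one or two degrees of freedom. If there is in truth no order effect, power at n = 40 is about 1 to 4 points lower, with centring at the low end and the two added terms at the high end. Neither option removes carry-over that differs from child to child, and the plan should acknowledge this.
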